# 1 Synopsis

Title:	International non-randomized, single-arm, long-term follow-up study of patients with uncontrolled H yper T ension
Acronym:	EnligHTN II
Purpose:	The purpose of this post market clinical investigation is to further evaluate the safety and performance of the EnligHTN™ Renal Denervation System in the treatment of patients with uncontrolled hypertension.
Objectives:	
The objective of this clinical investigation will be to assess the EnligHTN™ Renal Denervation System in renal artery ablation for the treatment of uncontrolled hypertension.
 
Primary Objective:
 
 
• Mean reduction in office Systolic Blood Pressure at six (6) months across all subjects post renal denervation and within sub-groups
 
 
Secondary Objectives:
 
Safety
 
Acute (30 days post procedure):
 
 
• The assessment of peri-procedural events
 
 
Midterm (6 months):
 
 
• Assessment of renovascular safety as measured by new renal artery stenosis or aneurysm at the site of ablation
 
• Renal function change based on eGFR
 
 
Long term (2 and 5 years):
 
 
• Assessment of renovascular safety as measured by new renal artery stenosis or aneurysm at the site of ablation
 
• Renal function change based on eGFR
 
 
BP reduction
 
 
• Change in Ambulatory Blood Pressure parameters at 6 months
 
• Change in office Diastolic Blood Pressure at 6 months
 
• Percentage of subjects achieving office Systolic Blood Pressure < 140 at 6 month visit
 
• Change in Office and Ambulatory Blood Pressure parameters at 12, 24, 36, 48, 60 months post denervation
 

Design:	
This is a post market, prospective, multicenter, non-randomized, single arm study of the EnligHTN™ Renal Denervation System. Approximately 500 subjects with uncontrolled hypertension will undergo renal artery ablation at approximately 40 investigational sites located internationally and will be followed up to five (5) years post procedure.
 
The clinical investigation is anticipated to start in October of 2012. Enrollment is anticipated to end in September of 2013. Subject participation will be up to five (5) years post procedure. Clinical investigation completion in 2018.

Devices used:	
EnligHTN™ Renal Artery Ablation Catheter  EnligHTN™ RF Generator  EnligHTN™ Guiding Catheter (optional)
 
All devices used in this investigation, have received appropriate certification (and are market released in the geographies participating in this clinical investigation).

Patient Population:	
The patient population enrolled in this investigation will consist of male and female patients 18 years of age or older that meet all of the specified inclusion criteria and none of the specified exclusion criteria

Patient Screening	
Patient Screening:  Patients that will be treated at the investigational site will be screened by a member of the investigational team. Patients who do not meet the inclusion/exclusion criteria are not eligible to participate.
 
Patients meeting the inclusion/exclusion criteria will be fully informed about the investigation and will be asked to participate in the investigation. A duly signed and dated, Ethics committee (EC) and Sponsor approved, Patient Informed Consent (PIC) will be obtained.
 
A patient becomes a subject once he/she has been fully informed about the investigation, has agreed to participate, signed & dated the Patient Informed Consent (PIC) and therefore has been enrolled in the investigation.

Inclusion Criteria	
 
• Subject is <math>\geq 18</math> years of age at time of consent
 
• Subject must be able and willing to provide written informed consent
 
• Subject must be able and willing to comply with the required follow-up schedule
 
• Subject has office Systolic Blood Pressure <math>\geq 140</math> mmHg at confirmatory visit
 
• Subject has a daytime mean Systolic Ambulatory Blood Pressure <math>> 135</math> mmHg within 90 days prior to procedure
 
• Subject has established hypertension (diagnosed <math>\geq 12</math> months prior to baseline) and is on a guideline based drug regimen at a stable and a fully tolerated dose consisting of <math>\geq 3</math> anti-hypertensive medications (including 1 diuretic), or subject has documented drug intolerance to 2 or more of the 4 major classes of anti-hypertensives (ACE/ARB, Calcium Channel Blockers, Beta Blockers, or diuretic) and is unable to take 3 anti-hypertensive drugs.
 

Exclusion Criteria	
 
• Subject has significant renovascular abnormalities such as renal artery stenosis <math>> 30\%</math>
 
• Subject has undergone prior renal angioplasty, renal denervation, indwelling renal stents, and/or abdominal aortic stent grafts
 
• Subject has hemodynamically significant valvular heart disease as determined by study investigator
 
• Subject has a life expectancy less than 12 months, as determined by the
 

[figure not shown]
SJM CONFIDENTIAL AND PROPRIETARY

© 2012 – St. Jude Medical Cardiovascular Division: All rights reserved. No portion of this work may be reproduced in whole or in part without the express written permission of St. Jude Medical Cardiovascular Division.

Clinical Investigational Plan: EnligHTN II

	
Investigator
 
 
• Subject is participating in another clinical study which has the potential to impact their hypertension management (pharmaceutical/device/homeopathic)
 
• Subject is pregnant, nursing, or of childbearing potential and is not using adequate contraceptive methods
 
• Subject has active systemic infection
 
• Subject has renal arteries with diameter(s) < 4 mm in diameter
 
• Subject has an estimated GFR <15 mL/min per 1.73 m^2 using the Modification of Diet in Renal Disease (MDRD) formula
 
• Subject had a renal transplant or is awaiting a renal transplant
 
• Subject has blood clotting abnormalities
 

--	--

SJM CONFIDENTIAL AND PROPRIETARY

Visit	Enrollment / Baseline	Confirmatory	Procedure	Discharge <72 hrs	1M ±14d	6M ±30d	12M ±60d	24M ±60d	36M ±60d	48M ±60d	60M ±60d
PIS & PIC	X										
Inclusion/Exclusion	X	X-review for changes									
Medical History	X	X-review for changes									
Office Blood Pressure	X	X		X	X	X	X	X	X	X	X
Physical Assessment	X	X-review for changes		X	X	X	X	X	X	X	X
24-h Ambulatory Blood Pressure	X-performed w/in 90 days of procedure	X-repeat if there are medication changes				X	X	X	X	X	X
Discharge Blood Pressure				X*							
***Echocardiography (TTE)		X			X	X		X			X
NYHA Assessment	X				X	X		X			X
Serum creatinine		X				X	X	X			X
Estimated GFR		X				X	X	X			X
Hemoglobin A1c		X				X					
Fasting Glucose		X				X					
Fasting Insulin		X				X					
Urine albumin-to-creatinine ratio		X				X		X			X
Medications Log	X	X-review for changes		X	X	X	X	X	X	X	X
Quality of Life questionnaire		X			X	X		X			X
Renal Artery Anatomy Evaluation		X – if not performed w/in 90 days	X			X		X			X
Pregnancy Test (urine / blood)		X									
Renal Denervation Procedure			X								
Adverse Event	**	**	**	**	**	**	**	**	**	**	**
CIP Deviation	**	**	**	**	**	**	**	**	**	**	**
Withdrawal/ Termination			**	**	**	**	**	**	**	**	X
(*) monitored every 4 hours post procedure until discharge, or for a maximum of 24 hours (**) as applicable (***) Echo will be performed at 6 preselected sites											

## 2 Background

Hypertension or high blood pressure is a major risk factor for cardiovascular and cerebrovascular events. It is responsible for approximately one half of the coronary heart disease and two thirds of the cerebrovascular disease burdens. It is also the world's number one attributable risk for death. The global prevalence of hypertension has been increasing. An analysis indicated that more than one quarter (nearly one billion) of the world's adult population had hypertension in 2000. This is projected to increase to 1.56 billion affected individuals with a prevalence rate of 29% in 2025. This is a major public health challenge in both economically developing and developed countries.

Previous studies showed that drug therapy may reduce the risk of major cardiovascular events by about 20% and the risk of stroke by about 40% in patients with hypertension. However, these may not apply to all patients with hypertension. A large proportion of patients with hypertension still remains untreated or uncontrolled due to many factors. For patients with resistant hypertension despite the use of aggressive drug therapy, which includes at least 3 anti-hypertensive drugs with a diuretic being one of these drugs, blood pressure management remains uncontrolled. In the general hypertensive population, the prevalence of resistant hypertension is estimated to be about 5% to 12%. In patients with co-morbidity, such as chronic renal failure or diabetes, the prevalence of resistant hypertension is even significantly higher. Hypertension is also mainly an asymptomatic disease, which could be difficult to have the patient understanding about the importance of complying and adhering to the lifelong drug therapy. Alternative approaches to control the blood pressure of these patients are urgently needed.

The kidneys represent the central homeostatic organ regulating blood pressure and blood volume. The sympathetic innervation of the kidney is implicated in the pathogenesis of hypertension through enhanced renin secretion and sodium re-absorption and reduced renal blood flow. Renal sympathetic afferent and efferent nerves run within and adjacent to the wall of the renal artery. Previous experimental functional studies showed that activation of the renal sympathetic nerve could cause increase and even spillover of the norepinephrine production, which results in the elevation of blood pressure, while renal denervation could reduce the norepinephrine level of up to 95%. Sectioning of the renal afferent nerves controlled the increased sympathetic activity in the posterior hypothalamus and allowed good control of the elevated blood pressure. In various experimental models, which include spontaneous hypertension, deoxycorticosterone-acetate-induced hypertension, obesity-induced hypertension and aortic coarctation models, the magnitude of the hypertension has been reduced and the renal blood flow has been increased during the observation period after renal denervation.

Radical surgical methods for abdominal, thoracic or pelvic sympathetic denervation (radical sympathectomy) have been used to treat patients with severe or malignant hypertension more than five decades ago. However, after the advent of modern anti-hypertensive drug therapy, radical sympathectomy was mainly reserved for non-responders of the anti-hypertensive drug therapy due to the extensive surgical procedure and technique, significant procedural time, long hospital stay (generally 2 to 4 weeks) and long recovery time (generally 4 to 8 weeks) in patients involved.

Percutaneous catheter-based methods deliver radiofrequency (RF) energy to the renal sympathetic nerves for the ablation-induced renal denervation. This minimally invasive and more localized approach allows for possibly much shorter procedural time, shorter hospital stay and shorter recovery time, which may benefit more patients with uncontrolled hypertension.

Recent clinical studies reported significant improvement of office blood pressure measurement in patients with resistant hypertension after the catheter-based renal denervation procedure (about -20/-10 mmHg, -25/11 mmHg, -23/-11 mmHg and -32/-14 mmHg at 1, 6, 12 and 24 months respectively from baseline systolic/diastolic blood pressures).

Further insights into mechanisms of hypertension control through renal denervation were published in a recent case report of a 59-year old patient with long-standing uncontrolled hypertension on a multi-drug regimen. The baseline renal norepinephrine spillover from both the left and right kidneys was approximately three times above the normal level, which indicated an elevated renal sympathetic neuronal efferent activity. Bilateral renal denervation resulted in a progressive and sustained improvement in the systemic blood pressure from 161/107 mmHg at baseline to 121/81 mmHg at 12 months and a decrease of the norepinephrine spillover by 48% from the left kidney and 75% from the right kidney at 1 month after the renal denervation procedure. The muscle sympathetic nerve activity as assessed by microneurography also reduced gradually to normal levels 12 months after the renal denervation procedure.

EnligHTN-I (ARSENAL) was a feasibility study to demonstrate the safety and efficacy of the St. Jude Medical Radiofrequency Renal Denervation System in the treatment of patients with resistant hypertension. This study is currently being conducted at four (4) investigational sites in Australia and Greece. Enrollment was completed on March 1, 2012 with a total of 46 patients having undergone the renal denervation procedure. Subjects will be followed for 24 months post procedure.

The one month clinical results from EnligHTN I were presented at the European Association of Percutaneous Cardiovascular Interventions, EuroPCR 2012 Congress May 15-18, 2012. Data was presented on 46 patients from four sites (60±10 years, 15 females/ 31 males) with a baseline average office Blood Pressure (BP) measurement of 176±16 / 96±14 mmHg, and an average of 4±0.6 anti-hypertensive medications. Fifteen (15) patients had a history of Diabetes Mellitus Type II. Median procedure time was 34.0 with a mean number of ablations completed on the right side of 7.7±0.8 and the left side of 7.4±1.4. One patient had the renal denervation procedure completed on the right side only due to tortuous anatomy. No vascular or renal artery complications were observed at the end of the procedure in any of the patients. At the time of discharge the average Blood Pressure measurement was 154/88 mmHg and at the one month time point the average office Blood Pressure measurement was 148/87 mmHg. The average systolic / diastolic Blood Pressure between baseline and one month was -28/-10 mmHg with 78% of the patients experiencing a ≥ 10 mmHg reduction in systolic Blood Pressure.

The three month clinical results from EnligHTN I were presented at the European Society of Cardiology (ESC) meeting on 28 August 2012. At the three month time point the average systolic / diastolic Blood Pressure difference between baseline and three month follow-up was -27/-10 mmHg with 80% of the patients experiencing a ≥ 10 mmHg reduction in systolic Blood Pressure. At 3 months, the mean systolic/diastolic ambulatory Blood Pressure difference between baseline and 3 months was -9.9/-5.4 mmHg.

## 3 Investigational Design

### 3.1 Purpose

The purpose of this Clinical investigation is to further evaluate the safety and performance of the EnligHTN™ Renal Denervation System in the treatment of patients with uncontrolled hypertension.

## 3.2 Objectives

### Primary Objective

The primary objective is to evaluate a mean reduction in office Systolic Blood Pressure at six (6) months across all subjects post renal denervation and within sub-groups.

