#### BP reduction

- Change in Ambulatory Blood Pressure parameters at 6 months
- Change in office Diastolic Blood Pressure at 6 months
- Percentage of subjects achieving office Systolic Blood Pressure < 140 at 6 month visit
- Change in Office and Ambulatory Blood Pressure parameters at 12, 24, 36, 48, 60 months post denervation

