### 4.8.3 Office Blood Pressure

Office Blood Pressure measurements will be recorded as the average blood pressure of three measurements at each follow-up visit. Measurements should be taken according to Standard Joint National Committee VII Guidelines / ESC and ESH Guidelines  (Refer to Appendix A for Office Blood Pressure instructions).

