### **7.3 Analysis Population**

All patients who have signed a Patient Informed Consent (PIC) will be considered enrolled in the study. However, Primary Analysis population will include those patients that have signed a PIC, and had the EnligHTN™ Renal Denervation System enter his/her body. The sample size of 500 are those subjects in the Primary Analysis population.

---

SJM CONFIDENTIAL AND PROPRIETARY

As Treated population will include all subjects in whom renal denervation was performed in a minimum of one renal artery per kidney (according to the Instructions for Use).

It is anticipated that there may be subjects who have enrolled in the study but are not included in the Primary Analysis population or As Treated population, such as:

- Subjects who are enrolled but do not meet baseline inclusion or exclusion criteria before the procedure; these are considered the screen failure population.
- Procedurally excluded populations will include subjects who have enrolled in the study and start the procedure, but do not have the EnligHTN™ Renal Denervation System enter his/her body, due to their anatomy, circumstances related to the procedure, or physician judgment.

Subjects that withdraw from the investigation will not be replaced in any analysis population.

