## **7.4 Data Analysis and Reporting**

In general data analysis will be performed across all subjects, as well as within each of three groups (Group A, B and C), based on Primary Analysis population unless otherwise specified.

The data collected will be presented using the appropriate summary statistics. Continuous data will be summarized using descriptive statistics (mean, number of observations, standard deviation, minimum and/or maximum values) and categorical data will be summarized using frequencies and percentages.

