### **7.4.1 Primary objective**

The mean reduction of office SBP at six (6) months of the study will be analyzed by:

1. Computing the reduction of SBP measurements at 6 months compared to baseline for each patient with data available in both time points.
2. Calculating the mean and standard deviation of the SBP reduction at 6 months

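### The primary 6-month SBP reduction averages only patients with a 6-month reading and leaves the 1-month reading unused, so it is biased if missing readings are related to early response

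*Combined protocol and SAP*

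**What the plan says.** Section 3.2 sets the primary objective as to "evaluate a mean reduction in office Systolic Blood Pressure at six (6) months across all subjects post renal denervation and within sub-groups". Section 7.3 does not make the analysis population depend on follow-up: the "Primary Analysis population will include those patients that have signed a PIC, and had the EnligHTN™ Renal Denervation System enter his/her body". The same section adds that "The sample size of 500 are those subjects in the Primary Analysis population", and that subjects who withdraw are not replaced. Section 7.4 then states that "data analysis will be performed across all subjects, as well as within each of three groups (Group A, B and C), based on Primary Analysis"; the set meant is the one just described.

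The primary calculation in section 7.4.1 has two steps. The first is "Computing the reduction of SBP measurements at 6 months compared to baseline for each patient with data available in both time points". The second is "Calculating the mean and standard deviation of the SBP reduction at 6 months". Section 7.4.2.3 uses the same calculation for the secondary blood pressure changes.

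A 1-month reading is scheduled. Table 1 and Appendix A list office blood pressure at 1 month, and section 4.8.3 says "Office Blood Pressure measurements will be recorded as the average blood pressure of three measurements at each follow-up visit". The blood pressure objectives cover 6 months and then "Change in Office and Ambulatory Blood Pressure parameters at 12, 24, 36, 48, 60 months post denervation"; none names 1 month. Section 4.9 also asks subjects who withdraw to attend a final visit that includes office blood pressure. Section 7 assigns neither reading a role in the primary estimate, and it names no missing-data method or sensitivity analysis for blood pressure. Section 7.4.3 only permits unspecified further analyses.

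**The concern.** The calculation in 7.4.1 recovers the mean for the Primary Analysis population only if subjects without a 6-month value have, on average, the same 6-month change as those with one. The protocol gives reasons to doubt this. Section 4.9 lists non-compliance and termination by the investigator among the reasons for leaving, and it provides for withdrawal because of an adverse event. Section 6.1 anticipates malignant or accelerated hypertension and symptomatic hypotension. All of these could be related to blood pressure response.

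In a single-arm study no comparator shares the bias, and in a descriptive study the estimate is itself the result. A reading that could inform the missing values is already scheduled for treated subjects about five months earlier.

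**Working it through.** **No figure in the plan to reproduce.** Section 7.2 disclaims a power analysis. The documents give no SD of change, no dropout rate and no correlation between visits. The sizes below are therefore conditional.

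**Step 1: exact identity.** Let *d* be the share of treated subjects without a 6-month value. Then

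paired-data mean − all-subject mean = *d* × (mean reduction in completers − mean reduction in leavers).

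| Share missing | Leavers 10 mmHg worse | 15 worse | 25 worse | 10 better |
|---|---|---|---|---|
| 5% | +0.5 | +0.75 | +1.25 | −0.5 |
| 10% | +1.0 | +1.5 | +2.5 | −1.0 |
| 20% | +2.0 | +3.0 | +5.0 | −2.0 |

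The sign follows the leavers' response. With no gap the bias is zero.

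**Step 2: a plausible SD.** Section 2 reports, for the feasibility study, a mean fall of 28 mmHg at 1 month with 78% falling at least 10 mmHg, and 27 mmHg at 3 months with 80%. If changes are roughly normal, SD = (mean − 10) / z:

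- 1 month: (28 − 10) / 0.772 = 23.3 mmHg
- 3 months: (27 − 10) / 0.842 = 20.2 mmHg

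An assumed SD of 20-25 mmHg is consistent with both. The 1-month figure also means that about 22% were poor early responders.

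**Step 3: missingness that follows the 1-month response.** Simulation used mean reductions of 28 mmHg at 1 month and 27 mmHg at 6 months (the 3-month figure stands in for 6 months). Further assumptions, none from the documents, were a correlation of 0.5-0.7 between the two changes and odds of missing raised 1.3 to 2.0 times per 10 mmHg poorer 1-month response.

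| Share missing | Overstatement by the paired mean | After using the 1-month value |
|---|---|---|
| 10% | 0.5 to 2.3 mmHg | within 0.1 mmHg |
| 20% | 1.0 to 4.3 mmHg | within 0.1 mmHg |

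The low end has SD 20, correlation 0.5 and odds 1.3; the high end has SD 25, correlation 0.7 and odds 2.0.

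**Step 4: scale.** The standard error is SD / √n. With 500 treated and 10% missing, n = 450 and 20/√450 = 0.94 mmHg. With 20% missing, n = 400 and 25/√400 = 1.25 mmHg. At the group minimums it is 20/√100 = 2.0 to 25/√100 = 2.5 mmHg for Group A, and 20/√50 = 2.8 to 25/√50 = 3.5 mmHg for Groups B and C.

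**Step 5: missingness that follows the unseen 6-month response.** Here the simulation assumed a true mean of 25 mmHg, SD 20, correlation 0.5-0.7, and odds of missing of e = 2.72 per SD, or √2.72 = 1.65 per 10 mmHg.

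| Share missing | Overstatement by the paired mean | Left after using the 1-month value |
|---|---|---|
| 5% | 1.0 | 0.5 to 0.7 |
| 10% | 1.8 | 0.95 to 1.4 |
| 20% | 3.5 | 1.9 to 2.7 |

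At 10% missing, 0.95/1.8 = 53% to 1.4/1.8 = 78% of the bias remains. The 1-month value therefore removes roughly 20-50% of it.

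**The case against.** The strongest reply is that the study is descriptive. Section 7.2 says that no hypothesis will be tested, no success threshold depends on 1 or 2 mmHg, and section 7.4.1 states openly which patients it averages. At 10% missing, even the upper figure is 2.3/27 = 8.5% of the assumed reduction. It is also smaller than the standard error in a group of 50. All of this stands. It limits the consequence to the accuracy of the reported estimate.

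The upper end is also demanding. Odds of 2.0 per 10 mmHg are 2.0² = 4-fold per SD at SD 20 and 2.0^2.5 = 5.7-fold at SD 25. Nothing in the documents supports that strength of selection, or 20% missing.

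A reader might infer that the plan breaks a promise to analyse every subject. The wording does not carry that: in sections 3.2 and 7.4 the phrase about all subjects mainly sets the pooled result against the group results. The mismatch rests on section 7.3, which defines the population without regard to follow-up.

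A reader might also take this mean to be the only efficacy result. It is not. Sections 3.2 and 7.4.2.3 list ambulatory pressure, diastolic pressure, the share below 140 and later changes. These do not escape the problem, however: the changes use the same paired rule, and the share below 140 counts only subjects with 6-month data.

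Finally, the near-zero bias in step 3 follows from construction, because missingness was generated from the very variable the model uses. Step 5 is the fair counterweight.

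**Conclusion.** The point holds in conditional form. Section 7.4.1 states a complete-case rule for a population defined without regard to follow-up, and it leaves an informative scheduled reading unused. If poorer early responders are more often missing, the overall mean reduction is overstated by about 0.5-2.3 mmHg at 10% missing and 1.0-4.3 mmHg at 20%. That can equal or exceed the standard error of 0.9-1.3 mmHg with 500 treated subjects. The figures rest on the assumed SD, correlation, dropout and selection strength given above.

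It would be tempting to conclude that the reported reduction will be inflated. The documents do not support this: they say nothing about how many subjects will lack a 6-month value or how those subjects responded. Nor would the model make the estimate free of bias, since it only partly corrects for missingness that depends on the unobserved 6-month value.

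**What to change.** In section 7.4.1, make the primary estimate, overall and within Groups A, B and C, the 6-month mean change from a repeated-measures model of office SBP at baseline, 1 month and 6 months. Use unstructured covariance and the Primary Analysis population. In addition:

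- State how office readings from the withdrawal visit in section 4.9 enter the analysis.
- State how deaths before 6 months are handled. Otherwise a model mean for the whole population implicitly assigns those subjects a 6-month pressure.
- Keep the paired-data mean as a supporting result.
- Add a delta-adjusted sensitivity analysis in which unobserved 6-month reductions are made progressively smaller than the model predicts.
- Report, overall and by group, the number without a 6-month value and their baseline and 1-month SBP.

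The cost is analysis-plan wording and one standard SAS procedure, with no new visits or data. There are two downsides: the main model assumes that missingness depends only on observed values, and the headline reduction may become slightly smaller. For subjects lost before 1 month, the model has only the baseline value to work from.
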